5.8.2 Follow-up of the subjects after the premature termination of treatment

Ending a subject's participation does not affect the normal management of the subject's illness in any way.

If there are serious adverse events, the investigator must notify the sponsor and monitor the subject for a month following the premature termination of treatment. If treatment is stopped prematurely due to a serious adverse event, a serious adverse event notification form will be sent by [contact]) to the sponsor. The serious adverse event will be monitored until it is resolved.

If a data and safety monitoring board (DSMB) has been created, this committee can specify and/or validate the monitoring methods.

5.8.3 Methods for replacing subjects, if applicable

A 10 % dropout rate of patients has been estimated and considered for the calculation of the number of subjects to be included.

5.8.4 Terminating part or all of the research

Le GHU Paris Psychiatrie et Neurosciences as sponsor or the Competent Authority (ANSM) can prematurely terminate all or part of the research, temporarily or permanently, upon the recommendation of a data and safety monitoring board in the following situations:

- first of all, if suspected unexpected serious adverse reactions (SUSARs) are seen in an arm being treated or if there is a discrepancy in the serious adverse reactions between the 2 arms being treated, and which require a reassessment of the benefit-risk ratio for the research [to be adapted].
- in the case of interim analysis: stopping treatment to demonstrate the efficacy of one of the arms being treated or on the other hand stopping due to futility
- likewise, unexpected facts, new information about the product, in light of which the objectives of the research or of the clinical programme are unlikely to be achieved, can lead Le GHU Paris Psychiatrie et Neurosciences as sponsor or the Competent Authority (ANSM) to prematurely halt the research
- Le GHU Paris Psychiatrie et Neurosciences as sponsor reserves the right to permanently suspend inclusions at any time if it appears that the inclusion objectives are not met.

If the research is terminated prematurely, the decision and justification will be given by the sponsor, Le GHU Paris Psychiatrie et Neurosciences, to the Competent Authority (ANSM) and to the CPP within 15 days, along with recommendations from the Data and Safety Monitoring Board (if applicable).

5.8.5 Screen failure

A subject who signed a consent form, but did not meet the inclusion/exclusion criteria is classified as a screen failure. Subject number, demographics and reason for screen failure will be recorded.

6 ELIGIBILITY CRITERIA

6.1 Inclusion criteria

- Adult patients admitted to an ICU with SAH related to a ruptured cerebral aneurysm occurring within the last 96 hours.
- Aneurysm successfully secured by surgical clipping or endovascular coiling

- Consent of the patient or, if not possible, from a proxy (emergency clause).
- Registration in a national health care system

6.2 Non-inclusion criteria

- Precritical modified Rankin Scale (mRS) > 2
- Nonaneurysmal SAH
- Delayed >96h admission after first symptoms of SAH
-
- Coma defined by GCS of 3-5 with untreatable aneurysm will be excluded"
- Known allergy to cilostazol
- Pregnancy
- Pre-existing major hepatic, renal, pulmonary or cardiac disease
- Concomitant use of one other anti-platelet and/or anticoagulant agent
- SAH diagnosed on Lumbar puncture with no evidence of blood on CT.
- Tutelage or guardianship

6.3 Recruitment methods

Patient's screening for recruitment will take place in all the participating ICUs.
An information form will be given to the patient or, if not possible, to a family member.

	Number of subjects
Total number of subjects chosen	630
Number of centres	9
Inclusion period (months)	42
Number of subjects/centres	79
Number of subjects/centre/months	1.9

7 TREATMENT ADMINISTERED TO RESEARCH PARTICIPANTS

7.1 Description of the experimental medication or medications

7.1.1 Experimental medication 1

Cilostazol 100mg tablets

Packaging type : blisters

Two times a day (every 12 hours) for 14 days, 28 tablets in total

Storage: room temperature

Shelf life: 3 years

Oral form if patient is able to swallow the tablet. If not, tablets will be crushed by the nurse in charge of the patient, and given by oral or enteral route through feeding tube if required. Of note administration of crushed tablet will be standardized at specific timing in each center. In case a patient can eat a meal, the delay between administration and meal will be of 30 minutes minimum

Of note a market authorization (Autorisation de Mise sur le Marché) is available in France for cilostazol in chronic arteritis but no marketed anymore since 2010 in France. The GHU Paris Psychiatry and Neurosciences pharmacy will import cilostazol which is also marketed in Europe. The blinding as well as the creation of a placebo will be subcontracted to a competent GMP establishment. The logistic will be centralized by the pharmacy of the GHU Paris and the pharmaceutical circuit will be co-constructed between GHU Paris and pharmacies of the different investigator centres (storage and delivery).

7.2 Description of the non-experimental treatment or treatments (medications required for carrying out the research)

7.2.1 Non-experimental medication 1

As recommended by French and European guidelines, a preventive medication of DCI by nimodipine has to be administered during the ICU stay. The posology, route (IV or enteral) and length of treatment is left to the discretion of the caring physician.

7.3 Description of the traceability elements that accompany the experimental medication or medications

Designated pharmacists responsible for the receipt, handling and dispensing of study drugs (active and placebo) will maintain study drug records during the study: details of how all phases of dispensing and withdrawal of unadministered drugs will be monitored and controlled, and the patient code/kit code correspondence will be described in the Pharmacy Manual to be established prior to the start of the study.

The investigator must maintain an accurate record of the shipment, storage, and dispensing of the study drug in a drug accountability log. An accurate record including the date and amount of study drug dispensed to each subject must be available for inspection at any time. A study CRA assigned to monitor the investigational site will review these documents once study drug has been received by the investigational site. Study drug will be accounted for on an ongoing basis during the study.

Further guidance and information for the final disposition of unused study intervention are provided in the Investigator Manual.

7.4 Authorised and prohibited treatments (medicinal, non medicinal, surgical), including rescue medications

Authorised treatments include every other preventive or curative treatments (medical or radiologic) for vasospasm and DCI, notably the use of milrinone, vasopressors for hypertension therapy (norepinephrine, dobutamine or epinephrine).

Unauthorised treatments include other antiplatelet agent or curative anticoagulation treatment. In case of an anticoagulation or antiaggregant is deemed necessary by the caring physicians, unblinding of the randomization will be realized and a 10 hours washout period will be advised before anticoagulation start if possible if the patient was randomized to the cilostazol arm.

Cilostazol dosage is modified by CYP3A4 inhibitors (clarithromycin, erythromycin, diltiazem, itraconazole, ketoconazole, ritonavir, verapamil, goldenseal and grapefruit) **or**

CYP2C19 inhibitors (e.g., Chloramphenicol, Clomipramine, Delavirdine, Fluoxetine, Fluvoxamine, Gemfibrozil, Imipramine, Isoniazide, Lansoprazole, Miconazole), thus these drugs will be prohibited during the administration of cilostazol. In case of a proton pump inhibitor will be prescribed, pantoprazole will be preferred as it has a limited to no effect on **CYP2C19 inhibitors**¹⁹. If any of the other drug is prescribed, cilostazol dosing will be reduced to 50 mg BID to mitigate interaction risks.

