4.2.5 Blinding methods and provisions put in place to maintain blindness

The physician investigator in each participating ICU will, after the patient fulfils the inclusion criteria and gives consent to participate in the CASH trial, use the online platform for data entry to randomize the patient, which in turn will allocate the participant to one of the two groups, from a pre-prepared randomization list.

The randomization will be held in an online platform for data entry, and as such, ensures allocation concealment by not releasing the randomization code until the recruitment is completed.

At the moment of randomisation in the e-CRF, visible to the investigator will only appear that "*the patient was successfully randomised*"; no other code will appear in the e-CRF. At the moment of randomisation, an email will inform the hospital pharmacy that a patient has been included and randomised; only the pharmacist will have access to the randomisation arm.

Both trial participants, care providers, and outcome assessors will be blinded after the patients' assignment to one of the trial groups. The double blinding will be provided by the hospital pharmacy of promotor establishment using placebo pills similar to commercial pills. Nurses in charge will be blind to the study as well as the physician and research technician in charge of outcome assessment.

In case of accidental loss of treatment, a form has to be completed with informations regarding the reason of the loss, the number of the patient and the number of days of treatment. The promotor will process the accident and will authorize or not the pursuit of the treatment. If the authorization is granted, the investigator site has to complete a form in the e-CRF for exceptional dispensing and will receive the code allowing the good dispensation according to the randomisation arm.

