7.5 Methods for monitoring compliance with the treatment

pharmacy visits will be planned, reporting:

- Number of tablets administered
- Number of tablets returned to the pharmacy

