12 STATISTICAL ASPECTS

12.1 Description of statistical methods to be used including the timetable for the planned interim analyses

CASH is a multicentre, double-blinded, randomised, placebo-controlled, parallel-group superiority trial in adult, using an adaptive group-sequential design, to demonstrate that cilostazol plus nimodipine is safe and superior to nimodipine alone will improve modified Ranking Score (mRS) at six months.

Two interim analyses for futility and efficacy are planned.

Populations

For the statistical analysis, the following populations are defined:

Population	Description
Intent-To-Treat (ITT) Population	The ITT population will include all randomised participants. ITT participants will be analysed according to the randomised treatment, regardless of the actual treatment received. All efficacy analyses will be performed on the ITT population.
Per Protocol (PP) Population	The PP population will include all participants in the ITT with at least 80% of doses received to define adherence to treatment. The PP population will be used for supportive analyses of efficacy measures.
Safety Population (SP)	The SP will include all randomised participants who received at least one treatment (active or placebo). The SP will be analysed according to the actual treatment received. This population will be used for safety analyses.

Description of the statistical methods, including the timing of planned interim analyses

The statistical analysis plan (SAP) will be developed and finalised before the database is locked.

Below is a description of the planned statistical analysis. Further details will be presented in the statistical analysis plan (SAP).

All statistical analyses will be performed with SPSS version 26 or RStudio. For analyses performed with RStudio, the script used will be provided.

The baseline is defined as the last evaluation performed before the start of the study treatment, day 1 (V1).

All data collected after the start of the study treatment are defined as post-baseline.

Baseline characteristics will be summarised by the treatment group. The mean and standard deviation (SD) or median and interquartile range (IQR) for skewed variables will be summarised for continuous measures.

The proportion in each category will describe categorical variables.

In addition, the 95% confidence interval (CI) will also be calculated as indicated.

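### Section 7.4 bans CYP3A4/CYP2C19 inhibitors, then sets a reduced cilostazol dose if one is given; the reduction is not reconciled with the 100 mg supply and has no described blinded procedure

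*Protocol*

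**What the plan says.** Section 7.4 lists CYP3A4 and CYP2C19 inhibitors and concludes "thus these drugs will be prohibited during the administration of cilostazol". The next sentence deals with acid suppression: "In case of a proton pump inhibitor will be prescribed, pantoprazole will be preferred". The paragraph then ends: "If any of the other drug is prescribed, cilostazol dosing will be reduced to 50 mg BID to mitigate interaction risks".

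Elsewhere the regimen has one level. Section 7.1.1 describes "Cilostazol 100mg tablets", given "Two times a day (every 12 hours) for 14 days, 28 tablets in total". The primary objective (Section 3.1) names 100 mg twice a day for 14 days and no other dose.

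On blinding, Section 4.2.5 blinds patients, care providers, nurses and outcome assessors by means of look-alike placebo, and says "only the pharmacist will have access to the randomisation arm".

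On adherence, the pharmacy visits in Section 7.5 report "Number of tablets administered" and tablets returned, while Section 5.2 records administration daily. Section 12.1 states: "The PP population will include all participants in the ITT with at least 80% of doses received to define adherence to treatment". Section 12.2.2 sets the same 80% against the doses prescribed over the 14 days.

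**The concern.** A site with a patient who is on, or needs, a listed inhibitor finds a ban and a dosing instruction in the same paragraph. The eligibility lists in Sections 5.1 and 6.2 do not mention these drugs, so a patient admitted on fluoxetine, for example, may be randomised and then meets both sentences at once. How study drug is given alongside an interacting medicine is a safety instruction and should have one reading.

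The statistical stake is the blind. The reduction is stated for cilostazol, but the people who would carry it out do not know who receives cilostazol. If only active patients were changed, a visibly altered dose would mark the active arm, and an unaltered dose in a patient on an inhibitor would mark placebo. This would happen in the ICU, while delayed cerebral ischaemia, vasospasm and cilostazol-related events are being recorded, and before the ICU-discharge mRS that Section 12.1 carries forward when the six-month value is missing.

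The smaller stake is the per-protocol set. If tablets are the record and doses are the criterion, a patient who follows a reduction exactly could be classed as adherent or non-adherent depending on the denominator.

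**Working it through.** **Ban against reduction.** Take the two possible meanings of the last sentence of that paragraph in turn.
- *Any listed inhibitor:* the sentence gives a dose for a combination that the paragraph has just prohibited.
- *Other proton pump inhibitors:* lansoprazole is on the prohibited list, while pantoprazole is only preferred. The overlap with the ban remains.

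Read as a contingency (prohibited, but act this way if it happens), the two sentences can coexist. The conflicts with the supply and the gap on the blind remain under that reading.

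**Reduction against supply.** Section 7.1.1: 2 tablets per day × 14 days = 28 tablets, which reproduces the stated total. No 50 mg tablet, matching 50 mg placebo or reduced-dose kit is described. Whether the 100 mg tablet can be halved is not stated.

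**Reduction against blinding.** Section 7.4 also covers a needed anticoagulant or antiplatelet. There the consequence for the blind is spelled out: the patient is unblinded (repeated in Section 4.2.6). For the dose reduction nothing is said, neither unblinding nor a blinded procedure.

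**Tablet count against the 80% threshold.** Inputs: 28 tablets (Section 7.1.1) and 80% (Sections 12.1 and 12.2.2). Assumptions not in the protocol: a reduced dose is half of a 100 mg tablet, halves are counted as halves, and the denominator is 28 whole tablets. With f full-dose days before the change:

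tablets = 2f + (14 − f) = 14 + f; threshold = 0.80 × 28 = 22.4.

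| Full-dose days f | Tablets | Share of 28 | Share of dose occasions |
|---|---|---|---|
| 0 | 14 | 50.0% | 100% |
| 4 | 18 | 64.3% | 100% |
| 7 | 21 | 75.0% | 100% |
| 8 | 22 | 78.6% | 100% |
| 9 | 23 | 82.1% | 100% |

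A fully adherent patient is below 80% on tablets for f ≤ 8 and above it for f ≥ 9. On dose occasions the same patient has 28 of 28 at every f. If instead unused halves are thrown away and not returned, dispensed minus returned also reads 28, although at f = 0 only 14 × 100 = 1400 mg of the planned 2800 mg was taken. The record could therefore err in either direction.

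**The case against.** The best defence is that this is ordinary contingency drafting. Section 7.4 treats antiplatelets and anticoagulants in the same way: not authorised, then what to do if one is needed. The protocol also uses the drug's name loosely for study treatment; the ban itself must bind both arms because prescribers are blinded. On that view nobody intends a change in the active arm only. Dispensing detail is deferred to a Pharmacy Manual, and a concomitant-drug restriction need not be repeated as an exclusion criterion.

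Much of this stands. A reader might infer that the reduction cannot be made blind. The protocol does not support that: active and placebo tablets look alike, nurses may crush them, and one identical instruction could be given for both arms without anyone learning the allocation. The accurate statement is that no such procedure is described.

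A reader might also infer that tablet counting misclassifies these patients. That is not established. Both per-protocol definitions speak of doses, administration is recorded daily, and no section defines adherence as tablets out of 28. The gap is a missing link between the record and the criterion.

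Nor do the documents show that the primary result is at risk. The primary analysis is by intention to treat, with discontinuation under treatment policy. The ICU-discharge mRS is rated by a blinded technician (Section 5.2), the six-month assessors are unaware of the arm (Section 8.1), and blinded adjudication of secondary endpoints overrides the investigator (Section 9.3).

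What the defence does not answer is which drugs the last sentence covers, how 50 mg is supplied when only 100 mg tablets are described, and why the blind is addressed for anticoagulants but not here. A Pharmacy Manual cannot settle which protocol sentence governs.

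**Conclusion.** The point holds as a failure to reconcile the text, with a specific risk to the blind. Section 7.4 is ambiguous between a ban and a dose rule. The dose rule does not match the described product or the regimen in the objective, and it is worded for one arm with no blinded procedure given. The active-only consequence depends on a literal reading; the documents neither require that reading nor close it off.

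The adherence point is secondary and conditional. The range of 50% to 78.6% against 100% rests on half-tablet dosing and a denominator of 28 whole tablets, and concerns only the supportive per-protocol analysis. Membership of the ITT population and the sample size are unaffected. The protocol does not say how many patients would be given a listed inhibitor, so no count of affected patients can be offered. No view is taken on which clinical rule or dose is right.

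**What to change.** 1. The sponsor should reconcile the sentences of Section 7.4 with each other and with Sections 6.2 and 7.1, and say which drugs the last one covers. The clinical content is for the sponsor to decide.
2. Whatever rule is kept should be worded for study drug and applied identically to active and placebo, without unblinding. Section 7.1 and the supply should be consistent with it in both arms.
3. Sections 7.5 and 12.1 should count per-protocol adherence as prescribed dose occasions taken, in line with Section 12.2.2, using the daily administration record. Tablet counts can remain as accountability data.

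The cost is wording in the protocol and pharmacy manual, and perhaps minor packaging work if a reduced dose is kept. No extra patients or procedures are needed. The small downside is that some placebo patients would have an inert dose changed.

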7.5 Methods for monitoring compliance with the treatment

pharmacy visits will be planned, reporting:

- Number of tablets administered
- Number of tablets returned to the pharmacy

8 ASSESSMENT OF EFFICACY

8.1 Description of parameters for assessing efficacy

Primary outcome

It is the Modified Rankin score (mRS):

It will be assessed at 6 months by physicians, physical therapists or research assistant or research nurses who would have been specifically trained to pass this score and who will be unaware of the trial-group assignments, during a face-to-face interview with patient. This structured interview will strengthen the interrater agreement (17)

Methods for secondary assessment criterion collection

At the 6 months interview and after collection of the mRS, one will proceed to the assessment of

- The SAHOT score (Appendix 2). For facilitating its collection and reduce time of the consultation, the SAHOT questionnaire will be sent to the patients before the 6 months face-to-face interview.
- MOCA score at 6 months (Appendix 3), which will be passed during the 6 months face-to-face interview by the trained investigator.
- Return to work at 6 months
- Activities of Daily Living (ADL) at 6 months (Appendix 4) and Instrumental Activities of Daily Living (IADL) at 6 months (Appendix 5), which will be passed during the 6 months face-to-face interview by the trained investigator.

Radiological endpoints will be collected daily during the ICU stay. Delayed cerebral ischemia is defined in the section 4.1.2 Highest velocity in the mean cerebral artery evaluated in tCD will be collected when available. MR/CTA DSA vasospasm will be scored as mild, moderate or severe according to the narrowing of the cerebral arteries.

8.2 Anticipated methods and timetable for measuring, collecting and analysing the parameters for assessing efficacy

Efficacy will be assessed with help of the mRS at 6 months, during a structured face-to-face interview of the patients which will involve one of the physicians, physical therapists, research assistants or research nurses of any participating centre. The organisation of the structured "CASH" protocol, version 2.1 of 04/04/2025

face-to-face interview will be as similar as possible between centres. During this M6 visit, the secondary outcomes- related scores will also be collected:

- SAHOT
- MOCA score
- Activities of Daily Living
- Instrumental Activities of Daily Living
- Return to work

During hospital stay, other parameters evaluating efficacy will be prospectively collected and reported on the e-CRF:

- Length of stay in the ICU
- Length of hospital stay
- 28-day mortality

9 SPECIFIC RESEARCH COMMITTEES:

Dénomination anglo-saxonne	Dénomination française	Caractéristiques
Independent Data Monitoring Committee (IDMC) or Data Safety Monitoring Board	Comité de surveillance indépendant (CSI)	Membres indépendants de l'investigateur
Steering Committee	Comité de Pilotage Comité Scientifique	Investigateurs, promoteur...
Endpoint Adjudication Committee	Comité de validation des évènements critiques	Travail en aveugle

Note: the Data Safety Monitoring Board (DSMB) is described in section 10.

